Group Fitness activities, however, do not typically include much interaction between participants. PlayFit, in contrast, includes a more intensive social interaction by focusing on team-based gameplay, yet designed to reduce competitiveness and maximize enjoyment. In most group fitness classes, social interaction is optional and the activities are not typically designed to be inherently enjoyable. PlayFit, by comparison, requires social interaction and taps into a powerful source of enjoyment - play. A worldwide survey by the furniture company IKEA observed that physical play was rated, by children, as more enjoyable than even television or video games [67]. Despite the importance of play to the human experience, few adults play sports [49] and few studies noted in meta-analyses of physical activity have applied aspects of play to adult physical activity promotion [68].

**What could occur if PlayFit outperforms Group Fitness classes?** We believe that three things would occur. First, fitness centers would offer programs such as PlayFit, in order to maximize social engagement, which fitness centers already use to help members make new friends which help people maintain their membership longer [69]. PlayFit is designed to be used on a basketball court, which is present in many fitness centers. We would make the protocol publicly available, in the public domain for free, to encourage its use. Second, it may lay the foundation for changing advice to patients from providers. Rather than focusing simply on the amount of activity and intensity of activity, providers could encourage patients to focus on how enjoyable the activity is to their patients. Third, it may lay the foundation for a change in exercise prescriptions to include a focus on enjoyment. At the present time, exercise prescriptions focus on frequency, intensity, type (moderate v. vigorous) and time (duration) [70]. Fourth, the design elements adapted for PlayFit—modifying where the intervention takes place, targeting whom the intervention takes place with, and altering what is done during the intervention—could be applied to other preventive health behaviors, such as healthy eating, to further refine interventions [42, 71-74].

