### **7.2.8 Randomization.**

Once eligible participants who sign the informed consent and completed the baseline questions, research staff at each site will randomize the participant into one of two groups (group fitness, PlayFit) in a one-to-one ratio based on the following stratification factors: age (over and under 35) and gender. The randomization will be performed through REDCap, but participant will not be informed of the group assignment until the accelerometer has been received and the baseline online surveys have been completed. At that point, a project staff member will contact the participant to review the randomization assignment (group fitness, PlayFit) and orient the participant to the program, by explaining how sessions tend to run, what to bring, reviewing possible locations, discussing frequently asked questions and answering any additional question the participant may have. Additionally, the participant will be given the option to install the TeamSnap phone application in order to receive exercise session confirmation and cancellation notifications.

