### **7.2.9 Group A. PlayFit – up to 4 times weekly**

This condition includes up to four times weekly, instructor-led, modified sports. Participants will be instructed to begin at a low pace and will gradually increase their intensity over time. PlayFit sessions start with a brief warm up period of “catch”, with a partner, using the piece of sports equipment of the day (e.g., ball, Frisbee), followed by alternating 10-minute periods of play and short water breaks. The warm-up and breaks encourage socializing. PlayFit classes, similar to Group Fitness classes (above), will be offered at multiple times during the day, similar to offerings at health clubs, to overcome scheduling barriers. The instructor who oversees the session will provide a minimal level of instruction on the basics of each sport during the warm-up, as well as explain 1-2 key movements per sport (e.g., using the instep of the foot for passing in soccer). The sports include soccer, using a lightweight volleyball, and 4 other modified sports that all use the rules of Ultimate Frisbee (Team Handball, Netball, Ultimate Football), including: 1) two steps only after catching, 2) change possession after dropping, 3) no contact with passer, and 4) no goalie (if using a net). Each day, the instructor will divide players randomly into sides and the instructor will also play, as in Group Fitness, to assure that the culture of non-competitive play is kept. If the score is lop-sided (e.g., 6-0), the instructor will switch two team members during one of the breaks. A brief period of “catch” at the end allows for cool-down and more socializing. Of note, the same fitness instructors will instruct PlayFit and Group Fitness, to control for the instructor effects. Sport modifications are as below. In addition, attendance will be recorded by the group leader at each session. Sessions will be offered up to 4 times per week. Participants will be sent a reminder notification for each confirmed, instructor-led session via the TeamSnap phone application.

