To assess intervention fidelity (i.e., that the amount and intensity of physical activity provided in each exercise condition is the same), a random sample of participants in each group and at each site will wear an ActiGraph GTX-3 accelerometer during up to five (5) 1-hour sessions of PlayFit or Group Fitness. Random numbers will be assigned to each participant at site "A" in intervention condition "1" using Excel. For example, a group of 40 participants at site "Hershey and" intervention condition "PlayFit" will each be assigned a random number from 1-40. The first 20% of participants at each site (i.e., those assigned numbers 1-8) will wear an accelerometer during that exercise session. Study staff will bring the devices to the session and provide them to the participants randomly selected for that exercise session. Following the 1-hour session, study staff will collect the devices and ask the participant to rate the perceived intensity level of the exercise session. The participant may decline to wear the device. For participants that decline to wear the device, study staff will go to the next random participant on their list and ask this participant to wear the device during the 1-hour session.

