### 7.2.10 Group B. Group Fitness – up to 4 times weekly

This condition is designed to represent a standard of care, as instructor-led group exercise classes are common at most fitness centers. Many fitness centers include multiple group exercise classes, although these differ somewhat from location to location. Participants will be instructed to begin at a low pace and will gradually increase their intensity over time. One of our Consultants is an exercise physiologist who creates and tests new fitness programs for Les Mills (New Zealand), the creator of Body Pump™ and other widely used programs [47, 79]. While men have been historically less interested in group fitness, this is no longer the case. The International Health, Racquet & Sports Club Association reported in 2016 that 38% of group fitness participants were men [44]. The Consultant has selected a set of 5-7 MET classes from common fitness centers to match the expenditure level of PlayFit. These classes will be included in a week-by-week plan for participants in the Group Fitness condition. In addition, subjects will be encouraged, at baseline, to ask questions of the fitness instructor at the beginning and/or end of the classes, as this is the standard of care at fitness centers. In months 1-2, participants will be encouraged to join the back of the group and leave early (e.g., after 30 min), until their fitness has improved. These classes will be offered at multiple times during the day, similar to offerings at health clubs, to overcome scheduling barriers. As group fitness classes are attended more by women than men, to limit the possibility of lower adherence in men to group fitness, the Consultant will be designing the intervention, based on years of designing programs for Les Mills and running her own studio, so that it is as gender-neutral (and attractive to men) as possible. Group fitness classes are more commonly attended by women, but her experience shows that several movements can be incorporated that make the fitness classes more interesting to men: strength training, athletic movements (e.g., high knee runs, block jumps) and martial arts movements (e.g., kicks, jabs). These tactics tend not to alienate women, so they will be used to make the programs more satisfying to men, as groups will be equally comprised of men and women. Attendance will be recorded by the group leader at each session. Sessions will be offered up to 4 times per week. Participants will be sent a reminder notification for each confirmed, instructor-led session via the Team Snap phone application.

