## 8.3 Statistical methods

The analysis of the main outcome measure will be performed by intent-to-treat, in which changes between baseline and twelve (12) full months of exercise intervention participation will be compared by conditions. Student's t-test will be used, though adjustment may be needed for any variables not controlled through randomization. If it is determined that the groups, by chance, are significantly different on other covariates, then we will include those covariates in secondary analyses.

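### Both arms are delivered in groups, but the primary t-test treats participants as independent; any positive correlation within a site-by-arm group makes its p-values too small and its intervals too narrow

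*Combined protocol and SAP*

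**What the plan says.** The primary analysis (8.3) is by intention to treat on change from baseline to 12 months: "Student's t-test will be used, though adjustment may be needed for any variables not controlled through randomization". The adjustment foreseen there concerns covariates that differ between arms. Neither 8.2 nor 8.3 contains a site, group, session or instructor term, an ICC or a design effect.

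Allocation (7.2.8) is by individual: "research staff at each site will randomize the participant into one of two groups", "in a one-to-one ratio based on the following stratification factors: age (over and under 35) and gender". Site is not a stratification factor.

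Delivery is by group in both arms. On PlayFit, 7.2.9 says: "This condition includes up to four times weekly, instructor-led, modified sports". Section 7.2.10 justifies the comparator on the ground that "instructor-led group exercise classes are common at most fitness centers". Section 2.3 gives the mechanism: "PlayFit, by comparison, requires social interaction and taps into a powerful source of enjoyment - play". Section 8.2 attributes the expected 2.5-unit VO2max advantage to better attendance.

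Other facts that bear on the size of the problem:
- A group size of 40 appears only in an illustration of how accelerometer wearers are sampled ("a group of 40 participants at site", in 7.2.9 and again in 7.2.10).
- The COVID rules in 7.1, 7.2.9 and 7.2.10 cap attendance at 30 participants per session.
- The same instructors teach both arms, and sessions are offered at several times of day (7.2.9).
- The number of exercise sites is not stated. Section 18 says the project is not multi-site, but 7.2.8, 7.2.9 and 7.2.12 all refer to exercise sites or to each site, so section 18 probably means institutions.
- Enrolment is up to 470 (8.1). The 2019 cohort had no 12-month visits (7.1).

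**The concern.** Individual randomisation makes the arms comparable at the start. It does not keep outcomes independent once people are treated together. Members of one arm at one site share a pool of teammates or classmates and an arm-specific timetable. If one site's PlayFit group gels and another's fades, attendance and VO2max move together within each group. That variation between groups adds to the variance of the difference between arms, and the standard error of a Student's t-test leaves it out.

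What is at stake is the error rate of the primary comparison. The omission favours a false positive: a few groups that happened to work well could yield a significant result from an interval that is too narrow.

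**Working it through.** **The plan's own figure.** The 470 cannot be reproduced, because 8.1 and 8.2 give no SD, alpha, power or dropout for the RCT. Taking the 2.5-unit difference, 235 per arm and an assumed two-sided 5% test, the implied SD is 2.5 / [(1.960 + z) × √(2/235)]. This is 9.67 at 80% power (z = 0.842) and 8.36 at 90% power (z = 1.282), before dropout. Neither version includes a design effect.

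**Inputs.** Number analysed per site-by-arm group, m: not stated, so 10, 20, 30 and 40 are shown. ICC of the site-by-arm component: not stated, so 0.01, 0.02 and 0.05 are assumed. Nominal test: two-sided 5%, assumed.

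**Formulas.**
- Design effect: DE = 1 + (m − 1) × ICC.
- True error of the unadjusted test: 2 × [1 − Φ(1.96/√DE)].
- The correct interval is √DE times as wide as the reported one.
- Effective sample size: 470/DE.

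Example with m = 20 and ICC = 0.02: DE = 1 + 19 × 0.02 = 1.38; 1.96/√1.38 = 1.67; true error = 9.5%; width ratio = 1.17; effective size = 470/1.38 = 341.

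Each cell gives results for ICC 0.01 / 0.02 / 0.05:

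| m | DE | True error, % | Interval width ratio | Effective size of 470 |
|---|---|---|---|---|
| 10 | 1.09 / 1.18 / 1.45 | 6.0 / 7.1 / 10.4 | 1.04 / 1.09 / 1.20 | 431 / 398 / 324 |
| 20 | 1.19 / 1.38 / 1.95 | 7.2 / 9.5 / 16.0 | 1.09 / 1.17 / 1.40 | 395 / 341 / 241 |
| 30 | 1.29 / 1.58 / 2.45 | 8.4 / 11.9 / 21.1 | 1.14 / 1.26 / 1.57 | 364 / 297 / 192 |
| 40 | 1.39 / 1.78 / 2.95 | 9.6 / 14.2 / 25.4 | 1.18 / 1.33 / 1.72 | 338 / 264 / 159 |

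At an ICC of zero nothing changes. The true error depends on m and the ICC, not on the total, so it does not rest on 470 being reached. The last column does, and is a ceiling.

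**Which correlation matters.** A simulation under no treatment effect (6 sites, 40 per site-by-arm group, 10,000 replicates) separates an effect shared by both arms at a site from one specific to a site-by-arm group. The t-test rejects:
- 5.0% of the time with no clustering;
- 4.5% and 3.8% with a shared site effect only (ICC 0.05 and 0.10);
- 9.3%, 14.3% and 26.1% with a group effect only (ICC 0.01, 0.02 and 0.05);
- 14.0% with a shared effect of 0.05 plus a group effect of 0.02.

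So the shared part is harmless, or slightly conservative, and only the site-by-arm part inflates the error. In a companion simulation with 39 per group and a group effect of 0.01, 0.02 or 0.05, a site-paired t-test rejects 5.1%, 5.4% and 5.0%.

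**The case against.** The strongest reply is that the documents do not establish how large the problem is.

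- **No ICC is given.** If the site-by-arm component is zero, the t-test is valid. This stands. But the plan gives no reason to expect zero, and its hypothesis that social play drives attendance points the other way.
- **Site and instructor appear crossed with arm.** Randomisation is done at each site and the same instructors teach both arms. Shared venue effects and the COVID stoppages largely cancel in the comparison. This stands, and it narrows the point to the site-by-arm component.
- **Groups are not fixed.** Sessions run at several times, PlayFit sides are redrawn each day, and orientation covers possible locations. This weakens correlation at session level and means the unit must be defined. People in one arm at one site still draw on the same companions and timetable.
- **The analysed groups may be small.** Enrolment of 470 is a maximum, the 2019 cohort has no 12-month data, and there are separate cohorts. This stands, and is why the table starts at 10 per group.
- **The target of inference could be the groups actually run.** That is a legitimate but narrower question. The plan's aim of informing what fitness centres should offer (2.3, 12.2) reaches beyond those groups.

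A reader might infer that the trial runs in groups of about 40, so that the true error is 10% to 25%. The documents do not support that. Forty is only an illustration in the fidelity-sampling rule. The cap of 30 is per session, so it neither confirms nor excludes a roster of 40.

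**Conclusion.** The omission is certain: the primary test and the sample size make no allowance for correlation arising from group delivery. The direction follows if the site-by-arm correlation is positive, which the plan's mechanism makes likely but which the documents do not prove. It would be too strong to say that the error rate definitely exceeds 5%, or that any clustering by site or instructor inflates it.

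The size is conditional on two unstated quantities. Over ICCs of 0.01 to 0.05, the true error runs from 6.0% (10 per group, ICC 0.01) to 25.4% (40 per group, ICC 0.05). For groups of 10 to 20 it lies between 6.0% and 16.0%. Because this is the primary comparison and the remedy is inexpensive, the plan should deal with it before the analysis.

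**What to change.** **Section 8.3.** Define the group unit as site by arm, within cohort, and say how a participant who uses more than one location is assigned. Replace the t-test with a linear mixed model for 12-month VO2max, and likewise for MVPA. Adjust for the baseline value, age stratum, gender and site, with a random site-by-arm group effect and Satterthwaite or Kenward-Roger degrees of freedom. Including the baseline value keeps the information that the planned change score uses.

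**If there are too few sites** to estimate the group variance, report a site-paired analysis of arm differences, plus a sensitivity analysis that widens the standard error for assumed ICCs of 0.01 to 0.05.

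**Section 8.2.** State the assumed ICC and group size, and restate the detectable difference with the resulting design effect, without enrolling more participants. At unchanged power the detectable difference grows by √DE. For example, if 470 was sized for 2.5 units, 20 per group and an ICC of 0.02 make it 2.5 × 1.17 = 2.9, before any loss of degrees of freedom.

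**Cost.** Revised wording, one random term and a group identifier for each participant; attendance is already logged at each session. The downside is a wider interval and fewer degrees of freedom. With 6 sites, for instance, the site-paired comparison has 6 − 1 = 5.

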# 9.0 Confidentiality, Privacy and Data Management

## 9.1 Confidentiality

### 9.1.1 Identifiers associated with data and/or specimens

See the Research Data Plan Review Form

#### 9.1.1.1 Use of Codes, Master List

See the Research Data Plan Review Form

#### **9.1.2 Storage of Data and/or Specimens**

See the Research Data Plan Review Form

#### **9.1.3 Access to Data and/or Specimens**

All project personnel (PI and project staff will have access to the data.

#### **9.1.4 Transferring Data and/or Specimens**

Not applicable. Data will not be transferred.

### **9.2 Subject Privacy**

See the Research Data Plan Review Form

## **10.0 Data and Safety Monitoring Plan**

We will work closely with our Data and Safety Monitoring Board (DSMB) to conduct biannual reviews of our procedures and data that is collected. All issues raised will be expected to be resolved no later than the time of the next meeting.

### **10.1 Data that are reviewed**

The DSMB will review no less than the following elements to assure compliance with the study protocol and to assure the quality of the data collected. They will review: consent forms, adverse events, outcome measures (e.g., V02max, accelerometry). Findings will be presented at a meeting attended by investigators and staff so all team members are aware and can be actively involved in a possible remediation plan.

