Subjects will complete a maximal test on a treadmill using a single maximal graded treadmill test, using a Bruce protocol and ECG or heart rate monitoring [1] using a metabolic measurement system, such as a COSMED, Parvomedics or other system. Each subject will be hooked up to mask that will collect their expired gases. They will also be connected to the Quinton Q-Stress ECG machine to monitor heart rhythms or they will wear a polar heart rate monitor. Each test will use an incremental exercise test method and subjects will be instructed on how to complete each test. They will also be instructed on how to use the Borg Rated of Perceived Exertion (RPE) scale (6-20). The test will be stopped when  $>2$  mm ST depression are noted on ECG or limited by symptoms. Speed and incline will be adjusted upwards in 3 minute increments consistent with the Bruce protocol.

Samples of gas from each 30-second period will be collected and compared to determine when steady state has been achieved, which is typically in the last 60 seconds of each 3-minute stage. The four criteria that will be used for stopping the test, consistent with when VO2Max has been achieved are 1) plateau in oxygen consumption as workload increases, 2) a respiratory exchange ratio (RER) of greater than 1.05 to 1.15 and 3) a heart rate that is within 10 to 12 beats of the age predicted maximum heart rate (220 - age) or 4) limited by symptoms or > 2mm ST elevation on ECG.

Clinical staff are present to both perform and supervise the individuals, to ensure safety. Testing will be overseen by [name], exercise physiologist and Lab Director.

During this visit, subjects will be provided with explanation about how and when to wear the accelerometer. They will be asked to wear it while awake for 7 days, rather than just when they are active. They will be shown how to wear it, on the waist, so that it captures movement appropriately. Participants will be emailed or called after 48-96 hours to be sure they are wearing it and help troubleshoot in case of difficulty with the monitor.

Research coordinator will provide payment to subjects among the RCT for completing the baseline visit following receipt of the accelerometer.

Household members will not have a baseline visit. Instead, the summary explanation of benefits will be sent to the household member, and they will be given the opportunity to ask questions to study staff. Household members will not be compensated financially.

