### **10.5 Frequency of review of cumulative data**

Biannually, the DSMB will meet and review AE frequency and severity, by condition and make a determination as to whether any changes should be made to the study protocol, consent or adverse event reporting procedure.

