### **10.6 Statistical tests**

Chi-Square tests will be used to determine differences in specific adverse events between conditions, as these variables are percentages.

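### The protocol does not keep by-arm interim results from trial staff, or the arm from those who run the 6- and 12-month treadmill tests

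*Combined protocol and SAP*

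**What the plan says.** On monitoring, Section 10.1 lists the DSMB's material: "They will review: consent forms, adverse events, outcome measures (e.g., V02max, accelerometry". It then states: "Findings will be presented at a meeting attended by investigators and staff so all team members are aware", and adds that the team can take part in any remediation. The same section gives the purpose as protocol compliance and data quality. Section 10.5 says: "Biannually, the DSMB will meet and review AE frequency and severity, by condition". Section 10.6 adds: "Chi-Square tests will be used to determine differences in specific adverse events between conditions". Section 9.1.3 says: "All project personnel (PI and project staff will have access to the data".

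On testing, Section 1.2 ends the maximal treadmill test at volitional fatigue. Section 7.2.6 (RCT) gives four stopping criteria: an oxygen plateau, an RER threshold, a heart rate near the age-predicted maximum, and symptoms or an ECG change. On who runs the test it says: "Clinical staff are present to both perform and supervise the individuals, to ensure safety". Section 7.2.16 repeats the baseline procedures at 6 and 12 months.

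On allocation, Section 7.2.8 has research staff randomise through REDCap. The participant is not told the arm until the baseline accelerometer and surveys are in.

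**The concern.** Participants cannot be blinded to an exercise programme, so protection against differential measurement has to come from the people who measure and from control of interim information. VO2max from a test to fatigue depends partly on how hard the participant is urged on. The investigators developed PlayFit and expect it to do better (Sections 1.1 and 7.1). A tester who knows the arm, or a team that has seen which way results lean, could press one arm harder without meaning to. Instructors and staff who re-engage lapsed attenders (Section 7.2.13) could do the same, and attendance is the route by which the plan expects VO2max to differ (Section 8.2). A bias of this kind is not reduced by sample size and would be only partly visible afterwards.

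**Working it through.** **Reading the text.** Three questions decide the point.

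1. *Can by-arm results reach staff?* Section 10.1 sends findings to investigators and staff. Section 10.5 puts adverse events before the DSMB by condition, and 10.6 tests them between conditions. Section 9.1.3 opens the data to all project personnel. None of these provides a closed session, a restricted report or a pooled-only rule. By-arm disclosure is therefore not excluded. It is also not stated: 10.5 describes DSMB review only, and 10.1 does not mention arms.
2. *Are the follow-up testers masked?* Section 7.2.6 does not say so and 7.2.16 adds no such step. Every mask in the document is a face covering or a gas-collection mask. The only concealment, in 7.2.8, applies to the participant and ends after the baseline measures, so it does not cover the 6- and 12-month tests.
3. *Does the test leave room for influence?* Plateau, RER and heart rate limit the tester's discretion. RER (1.05 to 1.15) and heart rate (within 10 to 12 beats) are given as ranges, symptom limitation is an alternative end point, and no encouragement script is described. Some room remains.

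**Scale, as an illustration.** Inputs from the plan: up to 470 enrolled (8.1), 1:1 allocation (7.2.8), hence 470/2 = 235 per arm; a target difference of 2.5 units (8.2); Student's t-test on change (8.3). The plan gives no SD, alpha, power or dropout for the RCT, so the 470 cannot be reproduced. Taking two-sided alpha 0.05, the SD of change that would make 235 per arm just sufficient is

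SD = 2.5 / [(1.96 + z) × √(2/235)], with √(2/235) = 0.0923.

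- 80% power (z = 0.842): about 9.7
- 90% power (z = 1.282): about 8.4

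These are back-solved values, so I use an assumed range of 4 to 10. With no true effect and a between-arm measurement bias b:

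SE = SD × 0.0923; d = b / SE; false-positive rate = 1 − Φ(1.96 − d) + Φ(−1.96 − d).

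| Assumed SD | SE | b = 0.5 | b = 1.0 |
|---|---|---|---|
| 4 | 0.369 | 27% | 77% |
| 6 | 0.554 | 15% | 44% |
| 8 | 0.738 | 10% | 27% |
| 10 | 0.923 | 8% | 19% |

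Example, SD 10 and b = 1.0: d = 1.0/0.923 = 1.08, and the rate is 0.19. A bias of 0.25 would give about 6% to 10% over the same SDs. With fewer than 235 per arm analysed, the SE grows and all these rates fall.

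**The case against.** The strongest reply is that 10.1 describes quality control. Its stated purpose is compliance and data quality, and the meeting exists so that the team can correct problems. On that reading the findings are matters such as missing forms or faulty tests. This stands as the more natural reading. A reader might infer that staff are shown VO2max trends by arm twice a year; the documents do not support that, since no section says VO2max or accelerometry is summarised by arm for anyone. That by-condition adverse events reach staff is likewise an inference from 10.1 and 10.5 read together.

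Other points also stand in part:

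- No section says that the treadmill staff are given the allocation. It is also not withheld from them.
- MVPA is measured by a device, so the tester concern rests mainly on VO2max.
- The same instructors lead both arms (7.2.9), and re-engagement follows a 14-day trigger with up to five contacts, with no distinction by arm (7.2.13). These rules limit differential effort, though not its quality.
- Little interim VO2max existed in the two cohorts described in 7.1. The 2019 cohort had 6-month visits, halted by the pandemic, and no 12-month visits; the 2021 cohort's 6-month visits were not feasible. This weakens the concern about interim trends but not the concern about unmasked testers.
- RER and heart rate are measured during the test, so peak values by arm would allow a partial check on effort. It would be wrong to say that a bias could never be detected.
- A DSMB charter, if there is one, might already provide closed sessions. None is among the documents.

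**Conclusion.** The gap is real but is one of omission. The protocol does not exclude by-arm results from what staff see, and it does not keep the 6- and 12-month testers unaware of arm, for a primary outcome that depends partly on effort. The physiological criteria reduce the risk and do not remove it. The documents do not show that by-arm VO2max is disclosed or that any bias has occurred.

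No single figure for the harm can be defended. The range of about 8% to 77% rests on assumed biases, assumed SDs, two-sided alpha 0.05 and all 235 per arm analysed; it shows only that a modest bias could matter. I would class this as a cheap improvement.

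**What to change.** - **Section 10.1:** limit the meeting with investigators and staff to pooled data-quality and compliance findings. Keep every by-condition summary of outcomes or adverse events, including the results under 10.5 and 10.6, in a closed DSMB session.
- **Section 9.1.3:** bar project staff from by-arm outcome summaries until 12-month data collection is complete. Without this, a change to 10.1 alone leaves the same information open by another route.
- **Section 7.2.16:** do not give the existing lab testers the allocation, ask participants not to reveal it, and use scripted encouragement. The rule belongs here because the follow-up tests are the ones exposed; at baseline the participant does not yet know the arm.
- **Reporting:** give peak RER and peak heart rate by arm with the final results, as a check on effort.

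The cost is protocol wording, a short script and a note to participants. It uses existing lab staff, and the DSMB already includes a biostatistician (10.4). The DSMB still sees everything, so its safety oversight is unchanged. The downside is that staff see less interim detail. Masking will be imperfect, because some participants will mention their programme.
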